8.2.3 Intensity of Adverse Event

The Investigator must assess the intensity of each reported AE according to the following grading scale:

Confidentiality Statement

Table 3Intensity of Adverse Events

Mild:	Easily tolerated, not interfering with normal everyday activities
Moderate:	Interferes with normal everyday activities, but the subject is still able to function
Severe:	Incapacitating and requiring medical intervention

8.2.4 Relationship to Investigational Product and Relationship to Study Procedures

The Investigator must assess the causal relationship between the exposure to the IP (Nicotine pouch 1.0, Velo-NP and Zyn-NP) and each of the reported AEs, using the classification system and the criteria described below. The same assessment must be made separately to assess the causal relationship between the study procedures and each of the reported AEs:

- **Not related**: The temporal relationship of the adverse event to IP administration or study procedure(s) makes a causal relationship unlikely, or concomitant medication, therapeutic interventions, or underlying conditions provide a sufficient explanation for the observed event.
- Related: The temporal relationship of the adverse event to IP or study procedure(s) makes a causal relationship possible, and concomitant medication, therapeutic interventions, or underlying conditions do not provide a sufficient explanation for the observed event.

8.2.5 Expectedness

Any AE assessed as related to the IP (Nicotine pouch 1.0, Velo-NP, Zyn-NP) will be assessed for its expectedness. An AE will be regarded as "unexpected" if its nature or severity is not consistent with information already recorded in section 6.5 of the current Investigator's Brochure [36].

8.2.6 Follow-up of Non-serious and Serious Adverse Events

Any non-serious AE that is ongoing at the time of Discharge or early termination will be followed-up by the Investigator during the Safety follow-up period until it has been resolved, stabilized (i.e., no worsening of the condition), or an acceptable explanation has been found (e.g., a chronic condition). The follow-up of the ongoing non-serious AEs will be done via a phone call performed at the end of the Safety follow-up period. If the subject is not responding at the first phone call additional two attempts will be made, then subject will be declared lost to follow-up (see section 5.3).

Confidentiality Statement

Philip Morris Products S.A.	Clinical Study Protocol	Confidential
P5-PK-01-EXP	2.0, Approved	Page 60 of 98
P.1. 1. 01/2 0012500		

At the end of the 3-day Safety FU Period, all ongoing non-serious AEs will have the outcome documented as "unknown" and will not be followed-up by the Investigator. At the discretion of the Investigator, the subject will be referred to his General Practitioner to have his/her ongoing AEs addressed accordingly.

All SAEs will be followed up by the Investigator or designee after the end of the Safety follow-up period, until their resolution, stabilization (i.e., no worsening of the condition), or an acceptable explanation has been found (e.g., a chronic condition). In case the subject cannot be reached for additional information related to SAE(s), a total 3 attempts should be performed before the subject will be declared as lost to follow-up (see section 5.3).

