3 STUDY OBJECTIVES

3.1 Exploratory Objective and Endpoints

1. To describe the plasma concentration-time profile of nicotine and derived pharmacokinetic (PK) parameters of 4 variants of Nicotine pouch 1.0 nicotine pouches compared to Velo-NP and Zyn-NP in healthy smokers from a 30 minutes product use period.

Endpoints (Day 1 to Day 3)

- Background-corrected maximum plasma concentration [C_{max}]
- Background-corrected time to the maximum concentration [T_{max}]
- Area under the background-corrected concentration-time curve (AUC) from start of product use (T0), to all subsequent timepoints and extrapolated to infinity [AUC0-5min, AUC0-10min, AUC0-15min, AUC0-20min, AUC0-25min, AUC0-30min, AUC0-35min, AUC0-40min, AUC0-1h, AUC0-3h, AUC0-6h, AUC0-infinity]
- 2. To describe pharmacodynamic (PD) effects (subjective effects and related behavioral assessments) of 4 variants of Nicotine pouch 1.0 compared to Velo-NP and Zyn-NP in healthy smokers from a 30 minutes product use period.

Endpoints (Day 1 to Day 3)

- Score of cigarette craving by the visual analog sale (VAS)-craving assessment [VAS-C-15min, VAS-C5min, VAS-C10min, VAS-C15min, VAS-C20min, VAS-C25min, VAS-C30min, VAS-C35min, VAS-C40min, VAS-C1h, VAS-C3h, VAS-C6h]
- Score of in the moment product liking by the VAS-liking (in the moment) assessment [VAS-L_{5min}, VAS-L_{10min}, VAS-L_{15min}, VAS-L_{20min}, VAS-L_{25min}, VAS-L_{30min}, VAS-L_{35min}, VAS-L_{40min}, VAS-L_{1h}, VAS-L_{3h}]
- Score of overall product liking by the VAS-liking (overall) assessment
- Score of product satisfaction by the VAS- satisfaction assessment [VAS-S_{5min}, VAS-S_{10min}, VAS-S_{15min}, VAS-S_{20min}, VAS-S_{25min}, VAS-S_{30min}, VAS-S_{35min}, VAS-S_{40min}, VAS-S_{1h}, VAS-S_{3h}, VAS-S_{6h}]
- Score of product intention to use again by the VAS-intention to use again assessment [VAS-ITU_{30min}, VAS-ITU_{3h}]
- Subscale scores from the Product Evaluation Scale (PES)
- Scores from items of the Sensory questionnaire

Confidentiality Statement

Philip Morris Products S.A.	Clinical Study Protocol	Confidential
P5-PK-01-EXP	2.0, Approved	Page 31 of 98
B. 1 1		

3. To evaluate the safety and tolerability during the study

Endpoints (from Enrollment to EOS):

- Incidence of adverse events (AEs) and serious adverse events (SAEs)
- Incidence of product events
- Changes in electrocardiogram (ECG) from baseline (heart rate, PR, QRS, QT, QTcF interval)

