5.3 Lost to Follow-up

A reasonable attempt will be made to contact all participants needing to complete or resolve post-study activities (e.g., safety laboratory, physical examination, on-going AEs).

Two contacts will be made via contact information provided by the subject (e.g., telephone number, cell phone number, email address), allowing 1 day between attempts for response. The first contact attempt should take place within approximately 1-2 days of the participant's last visit to the investigational site. If contact is not possible, a follow-up letter will be sent to the participant, allowing approximately 5 business days from the time of delivery for a response. A progress note will be added in the data collection system for documentation. After a letter is sent, there should be no additional phone calls unless the participant has attempted to contact the investigational site and a return call attempt is made. If post-study follow-up has not been resolved within approximately 5 business days following delivery confirmation or the letter is not deliverable, the participant is considered lost to follow-up. This is documented in the progress note and outstanding AEs are updated. The date of lost to follow-up corresponds to the date of the end of study of the subject.

The Investigator or designee(s) will declare the subject lost to follow-up if the investigational site lost contact to the subject and the subject has reached the maximum number of study days (27 days).

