8.2.2 Period of Collection

AEs (including SAEs) will be collected from the time of ICF signature until the individual EOS for each subject.

Any AEs which occur during the screening period will be captured by the investigational site staff and assessed by the Investigator or designee(s) in order to establish relationship to study procedures.

During a 3-day Safety follow-up period new AEs/SAEs associated with IP use will be recorded and ongoing AEs/SAEs will be followed-up by the study site, as described in section 8.2.6.

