9 STUDY ACTIVITIES

The schedule of assessment can be found in Appendix A. Measurements not conducted at the exact time point but conducted within the given time window (if applicable) do not constitute a protocol deviation but an accepted variability for the given time point.

In general, if no start time for the procedures is provided, then the procedure can be performed at any time during the day.

The main objective for this study is the evaluation of the plasma concentration-time profile of nicotine and derived PK parameters. Therefore, the collection of blood samples for determination of plasma nicotine concentration should be as close to the schedule time as possible and should take precedence over any other assessments required at the same time.

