9.6 Safety Follow-Up Period

After discharge at Day 3, the subjects will enter a 3-day Safety follow-up period during which AE/SAEs associated with IP use reported by the subjects will be collected and the follow-up of AEs/SAEs will be conducted by the study investigational site as described in section 8.2.6.

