8.6 Adverse Events

All AEs occurring during this clinical trial will be coded using MedDRA® using the version specified in the DMP.

All AEs captured in the database will be listed in by subject data listings including verbatim term, coded term, product, severity, relationship to study product, and action taken; All adverse events will be summarized. Adverse events that occur after ICF and prior to the product test on Day -1 and those that occur during the safety follow up (FU) period (after discharge to safety FU visit) will be summarized separately under admission/safety FU period.

A study product use-emergent adverse event is defined as an AE that is starting or worsening at the time of or after study product administration. An AE that occurs during the washout period between study products is considered study product use emergent to the last study product given.

If the onset time of an AE is missing and the onset date is the same as the product administration date, the AE will be considered product use-emergent to the prior and current product. If the onset time of an AE is missing and the onset date does not fall on a product administration date, the AE will be considered product use-emergent for the last product administered. If the onset date of an AE is missing, the AE will be considered product use-emergent and attributed to each product on the study, unless the onset date is known to have occurred within or between specific product periods.

All PUEAEs will be summarized by product and overall. The number and percentage of subjects with AEs, SAEs (including deaths), and product events listed will be tabulated by

Statistical Analysis Plan Number CA36095

system organ class and preferred term. Summaries will also be presented for AEs leading to product discontinuation, AEs leading to study discontinuation, AEs by relatedness to product exposure (including expectedness) and relatedness to study procedures, AEs by severity, and AE by action taken related to the product. Tabulations will be performed for both the number of subjects experiencing an event and the number of events.

SAEs, if present, will also be listed. Applicable narratives will be included in the CSR.

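### AE incidence is an endpoint to end of study, but the only call set for the 3-day follow-up concerns non-serious AEs already ongoing at discharge or early termination

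*Protocol*

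**What the plan says.** The observation window is clear. Protocol 3.1 heads the safety endpoints "Endpoints (from Enrollment to EOS", and Protocol 8.2.2 states "AEs (including SAEs) will be collected from the time of ICF signature until the individual EOS for each subject". Protocol 4.4 defines EOS as the end of the Safety follow-up.

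The means of asking within the last part of that window is narrower. Protocol 8.2.6 begins "Any non-serious AE that is ongoing at the time of Discharge or early termination will be followed-up by the Investigator during the Safety follow-up period" and continues "The follow-up of the ongoing non-serious AEs will be done via a phone call performed at the end of the Safety follow-up period". Protocol 5.3 adds contact attempts, but again for a subset: "A reasonable attempt will be made to contact all participants needing to complete or resolve post-study activities".

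For events that start after discharge, Protocol 8.2.2 says that new product-associated events are to be recorded, and Protocol 9.6 says "AE/SAEs associated with IP use reported by the subjects will be collected". Neither names a call, a visit or a question. Appendix A marks AE/SAE recording for Days 4 to 6, with no footnote on method.

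SAP 8.6 summarizes follow-up AEs separately from the in-clinic ones and bounds that period as "after discharge to safety FU visit". The protocol has no such visit, and SAP section 9 does not list it as a change.

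**The concern.** An incidence is only as good as the asking behind it. Protocol 8.2.1 sets a sound standard: a consistent, open, non-directive question, put mainly face to face. After discharge there is no face-to-face contact unless a visit is scheduled, and none is. The one call that is scheduled is made to subjects who already have an open event. So some exposed subjects are actively contacted in follow-up, and the rest are observed only through what they choose to report.

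Two things are at stake. First, a follow-up AE that a subject does not think worth reporting is lost, although the endpoint claims to cover it. Second, a zero in the follow-up table could mean that nothing happened or that nobody asked, and the data would not show which. This matters more than usual because Protocol 2.1.2 says that NP 1.0 has not been tested in humans, and safety and tolerability is one of the stated objectives.

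**Working it through.** The documents give no figure to reproduce. The check sets the passages side by side and then asks what can be said about size.

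**Step 1. Who is asked in follow-up?**

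| Source | Who is covered | What is set |
|---|---|---|
| Protocol 8.2.6 | Subjects with a non-serious AE ongoing at discharge or early termination | One call at the end of follow-up, with two further attempts if there is no answer |
| Protocol 8.2.6, SAEs | Subjects with a known SAE | Followed beyond the period until settled |
| Protocol 5.3 | Subjects with something outstanding | Two contacts, then a letter |
| Protocol 8.2.2 and 9.6 | All, for new product-associated events | Recorded if reported; no contact named |
| Appendix A, Days 4 to 6 | All | AE/SAE recording marked; no method |
| SAP 8.6 | All, by implication | A follow-up visit that the protocol lacks |

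The first three rows have a mechanism but cover a subset. The last three cover everyone but have no mechanism in the protocol. No row provides both.

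**Step 2. Who falls in the gap?** Protocol 12.2.2 puts every subject with at least one NP 1.0 exposure, including the Day -1 product test, in the Safety population. That means the 24 randomized subjects, those stopped after the NP-1 test, and any alternates who took the test. All of them enter the 3-day follow-up. Those with no open AE have no described contact.

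**Step 3. How large could the effect be?** Let N be the exposed subjects, k those called, p the chance of a new follow-up AE (assumed equal in both groups) and r the share of such events that an uncalled subject reports unprompted. Assume also that the call picks up new events in those who receive it.

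- Expected count if all are asked: N × p.
- Expected count as written: k × p + (N − k) × r × p.
- Relative shortfall: (N − k)/N × (1 − r).

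This runs from 0 (r = 1) to (N − k)/N (r = 0). The documents give neither k nor r, so no percentage can be stated.

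**Step 4. Does it distort the product comparison?** With the 6-period, 6-sequence Williams design of Protocol 12.9.1 and SAP 3.1, and equal allocation (assumed), there are 24/6 = 4 subjects per sequence. Each product comes last in one sequence, hence in 4 of 24 subjects. A loss after the last use would then fall evenly on the six products, apart from chance and dropout. SAP 8.6 also tabulates follow-up events apart from the in-clinic ones. The main effect is therefore on absolute incidence.

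**The case against.** The best reply is that the gap is one of silence, not of intent. Nothing forbids calling other subjects. Protocol 8.2.2 says that new events will be recorded, Appendix A marks recording on Days 4 to 6 for all, and SAP 8.6 presumes a contact. Site procedures that we cannot see may supply one. The study is exploratory, and Protocol 2.3.3 describes the expected product effects as transient, which points to the supervised hours and not to Days 4 to 6.

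Much of this stands. A reader might infer that subjects without an open AE are never contacted; the text supports only that no contact with them is described. It also cannot be said that incidence will be understated, only that it can be. What does not fall away is that, followed as written, the two groups are observed differently and the SAP relies on a visit that is not there.

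A reader might also infer a larger gap in clinic. Tables 6 to 8 list AE recording as occurring during the visit, and Protocol section 9 says "if no start time for the procedures is provided, then the procedure can be performed at any time during the day". On that reading one interview before the first Day 3 use would comply, and both Day 3 uses (2 of 6 per subject) would be followed by no AE question. The documents do not support it as a finding. Protocol 8.2.6 needs AE status to be known at discharge, which an interview before the morning use could not give. The Product Evaluation Scale, which includes dizziness, nausea and bothersome side effects, is given 1 hour after each Day 3 use. Protocol 7.8.8 lets the investigator record such answers as AEs, although at discretion. Subjects also have scheduled contacts up to 6 hours after the afternoon use. The missing time in Table 8 is worth a clarifying line, no more.

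**Conclusion.** The point holds for the post-discharge period. The endpoint and the collection period extend to EOS, the only scheduled call concerns non-serious AEs already open at discharge or early termination, and other exposed subjects depend on spontaneous report. SAP 8.6 and the protocol must be reconciled on the follow-up visit.

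Follow-up AE incidence can be understated by an amount that the documents do not allow us to estimate. Any percentage would need an assumed rate of unprompted reporting. The effect is mainly on absolute incidence and on the separate follow-up summary. Between-product contrasts should be little affected if the sequences are filled equally and dropout is low. No hypothesis is tested, so no formal inference is at risk. A change is still worth making, because it is cheap and because safety in a first human study is what the follow-up is for.

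**What to change.** - **Protocol 8.2.6 and 9.6:** extend the existing end-of-follow-up call to every exposed subject, including alternates and those stopped after the NP-1 test, and ask the open question of 8.2.1. State one rule for unanswered calls, since 5.3 (two contacts and a letter) and 8.2.6 (a first call and two more attempts) differ.
- **Appendix A:** add a footnote to AE/SAE recording on Days 4 to 6 naming this call.
- **SAP 8.6:** replace the follow-up visit with the call as the end of the period.
- **Table 8, as a minor clarification only:** state that the Day 3 AE question is asked after the afternoon use and before discharge.

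The cost is protocol and SAP wording plus about one short call per exposed subject: 24 randomized subjects, and any others who took the product test, less those who would be called anyway. The site already makes this call for subjects with open events. Recorded AE counts may be slightly higher. No product use or clinical rule changes.

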8.3 Reporting of Serious Adverse Events

Any SAE observed during the period of collection in this study must be reported within 24 hours of first awareness to Sponsor, via email, having the SAE form attached.

As further information regarding an already reported SAE becomes available to any of the parties involved in this study, such follow-up information should be reported on a new SAE report form, marked as a follow-up report and submitted to Sponsor according to the same timelines as described above. The follow-up SAE report form must include the minimum information required for form completion and only changed/new information needs to be specified. Information provided in the follow-up SAE report form supersedes any information that was initially reported.

The SAE report form to be used in this study is provided as a separate document. All SAEs will also be recorded on the relevant CRF page, in addition to the SAE report form.

The Investigator or designee is responsible for submitting the relevant reports of SAEs that occur during the study to the IEC, according to local regulations and in accordance with the respective safety management plan (SMP).

8.4 Reporting of Other Events Critical to Safety Evaluations

The other abnormal findings discovered during different clinical assessments (e.g., ECG, physical examination, vital signs, body weight, safety labs results) should be evaluated for clinical significance by the Investigator/designee based on his/her medical judgement. All abnormal clinically significant test results or clinical examination findings should be reported as AEs and handled as described in section 8.2.

8.5 Reporting and Follow–Up of Pregnancies

8.5.1 Period of Collection and Follow-up

Pregnancies detected between the time of signature of the ICF and the time before first exposure to the IP will be considered a reason for screen failure. No pregnancy form will

Confidentiality Statement

Philip Morris Products S.A.	Clinical Study Protocol	Confidential
P5-PK-01-EXP	2.0, Approved	Page 61 of 98
B 1 . 1. 01 /2 001		

be filled in that case, however the diagnosed pregnancy must be captured in the screen failure page of the CRF.

Any pregnancy detected after first exposure to the IP must be reported by the Investigator within 24 hours. This also includes pregnancies spontaneously reported to the Investigator after the end of the study for a subject. A dedicated pregnancy form will be used to report reportable cases of pregnancy.

Any pregnancy that was potentially associated with exposure to IP (NP 1.0, Velo-NP, Zyn-NP) will be followed-up until an outcome is reached (e.g., normal delivery, spontaneous abortion, or voluntary termination) and also until 8 weeks after delivery. Any pregnancy complication, adverse pregnancy outcome or maternal complications will be recorded as an AE accordingly.

The procedure outlined in section 8.3 should be followed to collect pregnancy reports and provide any additional/follow-up information to Sponsor.

8.5.2 Reporting of Pregnancies

The Investigator is responsible for informing the responsible IEC of any pregnancy case that was reported during the study, as determined by local regulations.

8.6 Adverse Events Leading to Discontinuation

Subjects who are discontinued from the study because of an AE will undergo the early termination procedures (section 9.7), as soon as practical after discontinuation and will enter the 3-day Safety follow-up period.

Any AEs or SAEs that are ongoing at the end of the Safety follow-up period will be managed as described in section 8.2.6.

8.7 **Product Events**

Any occurrence of NP 1.0 product events should be actively collected during the study and documented by the study site. Nicotine pouch 1.0 product events will be categorized into:

- Nicotine pouches not extractable from can/sticking together
- Rupture of the nicotine pouch when using
- No release of flavor when using
- No release of nicotine when using, or
- Other

Furthermore, any product event that leads to an AE/SAE will follow the same processes as described in section 8.2.

Confidentiality Statement

Confidential Page 62 of 98

Related to QMS-0017588

